## **Ethical considerations**

The study protocol will be submitted for approval to the Regional Ethical Review Board in Uppsala and subsequently registered at the international registry of clinical trials, ClinicalTrials.gov. The parents of the infants will be informed about the study by specially trained personnel, both verbally and in writing, before the child is born or, whenever that is not possible, as soon as possible after birth. Upon agreement to participate, written informed consent will be obtained from the parents, before enrollment in the study. Additionally, the parents will be clearly informed about the possibility to leave the study any time they wish.

None of the studies published so far reported any adverse events by induced meconium evacuation, with the exception of a higher proportion of NEC (although not statistically significant), vomiting, nausea and bradycardia with the use of oral gastrografin (1,22), and a non-significant trend towards increased risk of NEC with the use of glycerine enemas or suppositories compared with no treatment (25). However, in the RCT study described herein, both health personnel involved in the participating infants' daily care and the investigators are going to closely monitor for possible adverse events. Possible adverse events could be: rectal bleeding (including occult rectal bleeding-induced anemia), fluid loss due to overstimulation of immature intestines of preterm infants or the opposite effect, namely intestinal absorption of given saline, leading to hypervolemia and electrolyte disturbances, mainly hyponatremia. A safety monitoring committee will monitor adverse events with predefined stopping rules. Early stopping criteria will be applied in case of medical instability, as mentioned above. Furthermore, the whole study will be discontinued in case of too obvious positive effect, making it unethical to deprive the control group of the intervention, or in case of severe adverse events.

The inclusion of study participants in other interventional studies could intervene with the outcomes intended to be investigated in the study herein, rendering it difficult to retrieve definitive conclusions. Thus, study participants will not be included in other interventional studies at the same time.

The intervention will be discontinued if the infant is transferred to another hospital, as mentioned before. The decision to transfer a study subject to home or other hospital unit will only be based on current criteria and will not be affected by the participation in the study. Study participation is not expected to delay the transfer to home hospital and prolong the stay at our NICU in Uppsala, unless a severe adverse event should occur.

### **Reporting and dissemination**

Following the study, data will be analysed by the research group and the results will be published in reviewed medical journals and possibly presented in a neonatology conference, hopefully during year 2023. It is difficult to provide a precise time schedule. Patient data collection is estimated to last about 4 years. Data analysis thereafter is time consuming and may last one more year until the whole project is completed and ready for publication. All the principal investigators will have free access to raw data and the right to publication.

### **Further specifications:**

Sepsis definition: positive blood, urine and/or CSF culture, clinical deterioration and laboratory inflammatory response\*.

A blood culture indicating growth of coagulase-negative staphylococci (CoNS) will be considered as false positive if following criteria are not fulfilled:

1. clinical symptoms
2. two separate blood cultures with the same antibiotic resistance pattern and/or central venous/arterial line prior to onset.
3. laboratory results indicating infection\*

Culture-proven sepsis will be further classified as early (<72 hours postpartum) or late (≥72 hours postpartum) onset and if caused by CoNS or not.

\* Laboratory inflammatory response (one of the following is needed):

1. LPK < 5 or > 20 ( $\times 10^9$  cells/L)
2. TPK < 100 ( $\times 10^9$  cells/L)
3. CRP > 15 mg/L

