## Study hypothesis

Regular intestinal lavage in preterm infants of GA between 22+0 and 26+6 weeks facilitates faeces evacuation, shortens the TFF and time to regaining of birth weight, thereby decreasing the risk of sepsis (through shorter intravascular access) and NEC.

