## **Allocation**

A blinded research coordinator will randomly assign eligible infants using a computer software-based randomization system (default) or sealed, numbered, and opaque envelopes (back-up), with a 1:1 allocation ratio, as soon as possible and not later than 24 hours from birth.

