## **Sample size calculation and estimated duration of the study**

Sample size calculation is based on the incidence of NEC, as the rarest of the events that will be studied, which is currently about 15% among extremely preterm infants at our unit, as mentioned above. For study power of at least 70%, confidence level of 5%, and an expected decrease of NEC incidence from 15% to 8%, each study arm should include about 100 participants (29). Each year, our unit treats about 70 infants born in GA 22+0 – 26+6. Supposing a participation rate of 70%, it is estimated that the recruitment period should last between 3 and 4 years, preliminarily starting during 2018. However, a recruitment period of maximum 5 years will be allowed.

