## **Exclusion criteria**

Infants with major dysmorphic features and major congenital anomalies, such as gastrointestinal disorders, as well as infants with circulatory instability during the first hours of life will be excluded from the study.

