### **Intervention**

The following intervention will be applied to the intervention group: specially trained pediatric surgeon will administer 10ml/kg pre-warmed (37°C) normal saline via a single-use rectal tube of size 6FR twice per day, aiming at a depth of maximum 10 cm/kg, starting after randomization and not later than 24 hours of age, and continued until full enteral nutrition of 170ml/kg/day is achieved or NEC diagnosis (Bell stage II or more) is established, whichever comes first. However, the intervention will be applied at a maximum of 2 weeks from birth. Besides, the intervention will be withheld in case of suspicion of infection or NEC but will be resumed if antibiotics are not introduced and discontinuation of feeds does not exceed 48 hours. Early stopping criteria include infection / sepsis or NEC suspicion necessitating prolonged discontinuation of feeds > 48 hours and / or antibiotics, circulatory instability or adverse events. The intervention will only be applied at the NICU of University Children's Hospital in Uppsala and will be discontinued if the infant is transferred to another hospital. Standard departmental guidelines will be followed regarding ventilation, choice of PN, invasive monitoring, and management of sepsis and/or necrotizing enterocolitis (NEC) for both the intervention and the control groups.

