## **Secondary outcomes**

Time to regaining of birth weight, growth, BPD, IVH, PDA, ROP, small intestinal perforation, sepsis, hyperbilirubinemia, mortality, adverse events, age at the time of discharge from hospital, number of days on PN, IFALD, and neurological development.

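### Pooled and early-onset sepsis carry no requirement that onset follow randomisation, so episodes before allocation would count and slightly dilute one secondary outcome

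*Combined protocol and SAP*

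**What the plan says.** The Secondary outcomes section names sepsis in a list ("small intestinal perforation, sepsis, hyperbilirubinemia, mortality, adverse events") and sets no limit on when an episode begins. Further specifications defines a case by positive culture, clinical deterioration and laboratory response, and then adds an age-based split: "Culture-proven sepsis will be further classified as early (<72 hours postpartum) or late (≥72 hours postpartum) onset". Both classes are timed from birth.

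Allocation takes place "as soon as possible and not later than 24 hours from birth", and the washout is given "starting after randomization and not later than 24 hours of age". The Study hypothesis states how sepsis should fall: faster feeding, "thereby decreasing the risk of sepsis (through shorter intravascular access) and NEC".

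Two provisions narrow the gap between birth and allocation, or who is in it. Exclusion criteria states that "infants with circulatory instability during the first hours of life will be excluded from the study", and Ethical considerations has parents informed "before the child is born or, whenever that is not possible, as soon as possible after birth". Infection is not an exclusion criterion.

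**The concern.** An outcome used to compare randomised arms should count events that the allocated treatment could influence. Up to 24 of the 72 hours in the early-onset class, as much as one third, can precede allocation. An infant who is septic in that time but circulatorily stable is eligible, and would enter the analysis as a sepsis event in whichever arm is drawn. In the washout arm such an infant may also receive little washout, because the Intervention section withholds it when infection is suspected and stops it when infection requires antibiotics.

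At stake is the sepsis estimate. Events that the treatment cannot affect are added to both arms, so the relative risk moves toward 1 and the comparison loses precision. Sepsis is named in the Study hypothesis, so readers will look at that estimate even though it is secondary.

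**Working it through.** **Timing.** Latest allocation is 24 h after birth, and early onset runs from 0 to 72 h after birth. Episodes from birth to allocation therefore fall in the early class and in the pooled total. Late onset starts at 72 h, at least 72 − 24 = 48 h after the latest allocation, so it holds none of them.

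**No figure to reproduce.** The plan gives no sepsis rate, effect or power for this trial: "Sample size calculation is based on the incidence of NEC, as the rarest of the events that will be studied". What follows only illustrates the size.

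**Inputs.**
- n = 100 per arm (Sample size calculation); two-sided 5%.
- C = 27.8%, the pooled control rate including pre-randomisation sepsis. It is the control rate in the observational glycerine enema study cited in Background, which is a different population.
- q, the share of infants with culture-proven sepsis before randomisation: assumed 1%, 2% or 5%.
- Washout halves sepsis after randomisation: assumed.

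**Formulas.** Post-randomisation control risk p = (C − q)/(1 − q), taken as equal in infants with and without earlier sepsis. Washout risk is p/2. Counted as written, each arm shows q + (1 − q) × risk. Power = Φ{[Δ − 1.96√(2p̄(1 − p̄)/n)] / √[(p₁(1 − p₁) + p₂(1 − p₂))/n]}.

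**Worked case, q = 2%.** p = (0.278 − 0.02)/0.98 = 0.2633; washout 0.1316. As written, the washout arm shows 0.02 + 0.98 × 0.1316 = 0.149, so the relative risk is 0.149/0.278 = 0.536. With Δ = 0.129 and p̄ = 0.2135, power = Φ[(0.129 − 0.1136)/0.0572] = 60.6%.

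| q | As written | RR | Power | Post-randomisation only | RR | Power |
|---|---|---|---|---|---|---|
| 1% | 27.8% vs 14.4% | 0.52 | 64.3% | 27.1% vs 13.5% | 0.50 | 66.5% |
| 2% | 27.8% vs 14.9% | 0.54 | 60.6% | 26.3% vs 13.2% | 0.50 | 64.9% |
| 5% | 27.8% vs 16.4% | 0.59 | 49.3% | 24.0% vs 12.0% | 0.50 | 59.9% |

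With a weaker assumed effect (RR 0.70) at q = 2%, power is 24.8% as written and 26.7% after the change. If 27.8% is instead all post-randomisation and q is added on top, power as written is 65.9%, 63.8% and 58.1%, against 68.0%.

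**Sensitivity to when the effect starts, q = 2%.** Suppose 2 points of control sepsis fall between randomisation and 72 h. Late-onset risk is then 26.3 − 2 = 24.3% in controls and half of that, 12.2%, with washout.

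| Count | Effect starts at once | Effect only from 72 h |
|---|---|---|
| Pooled, as written | 27.8% vs 14.9%, power 60.6% | 27.8% vs 15.9%, power 53.2% |
| Post-randomisation | 26.3% vs 13.2%, power 64.9% | 26.3% vs 14.2%, power 57.2% |
| Late onset (≥72 h) | 24.3% vs 12.2%, power 60.7% | 24.3% vs 12.2%, power 60.7% |

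In the right-hand column the post-randomisation washout rate is 2 + 12.2 = 14.2%, and the pooled rate is 2 + 0.98 × 14.2 = 15.9%. Under the same late-effect assumption, 1 point before 72 h gives 61.1% (post-randomisation) against 62.8% (late onset); 4 points gives 49.5% against 56.2%.

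Counting only post-randomisation episodes beats the pooled count in both columns. Whether it beats late onset depends on when the effect begins.

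**The case against.** **The plan is silent, not wrong.** The text never says that episodes before allocation will be counted. That is fair: the documents show a missing onset rule, not that such episodes will occur. But an analyst who applies the definition as written would count any that do.

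**The clean analysis is already planned.** Late onset is pre-specified and free of the problem. This stands, and it has support from the trial's own mechanism. Intravascular access can shorten only once parenteral nutrition stops, and the Feeding regimen targets full enteral nutrition within 5 days at 26–28 weeks and 7–10 days at or below 26 weeks. On that pathway an effect before 72 h is unlikely. A reader might infer that restricting to late onset throws away the gain from the correction. That follows only if washout reduces sepsis before 72 h; otherwise late onset does better (60.7% against 57.2%). Late onset is still only a subclass of the listed outcome, so it does not replace a rule for the pooled and early counts.

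**The size is assumed.** No pre-randomisation sepsis rate is given. Prompt allocation, information to parents before birth, the circulatory exclusion and the three-part case definition all point to a small number. At 1–2% the power difference in the main illustration is about 2 to 4 points. This stands.

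**The remedy is partial.** Infection present at allocation but first cultured later would still count, and the early class would span 48 to nearly 72 h depending on the infant. Both are true; neither is a reason to count episodes already diagnosed before allocation.

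**Conclusion.** The point holds as a minor gap in an outcome definition. That pooled and early-onset sepsis lack an onset rule is certain from the text. The size of the effect is not: the relative risks of 0.52 to 0.59 in place of 0.50 rest on an assumed q, an assumed halving, and a control rate from another population.

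Three stronger readings might be inferred, and the documents support none of them.
- Bias between arms: episodes before allocation are balanced in expectation, so they dilute and add noise without favouring an arm.
- Loss of planned power: sample size was set on NEC, so sepsis has no planned power to lose.
- Damage to the primary outcomes: nothing here bears on NEC or time to full feeds.

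**What to change.** Add to Further specifications:

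*Sepsis outcomes count only episodes whose first qualifying culture was taken after randomisation. All randomised infants stay in the denominator. A new episode in an infant with earlier sepsis counts; a repeat culture from the earlier episode does not.*

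Compare all post-randomisation sepsis with the χ² or Fisher test already planned in Statistical analysis. Keep the planned split as subclasses: early from randomisation to 72 h after birth, late from 72 h. Report the late-onset comparison alongside, since it best matches the hypothesised route through shorter intravascular access. List sepsis first cultured before randomisation by arm as a baseline characteristic, which will also show how large the issue was.

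The cost is a short addition and one baseline row; conduct of the trial does not change. Culture times should be in the unit's own records: Follow-up describes continuous registration of findings, and transfer is usually not before 28+0 weeks, which is 196 − 188 = 8 days after birth even for an infant born at 26+6. In the main illustration about 1, 2 or 4 fewer infants per arm of 100 would be counted at q = 1%, 2% or 5%. Infection present at allocation but cultured later would remain in the post-randomisation total.

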**Funding sources:**

The project herein will be funded by ALF sources (ALF stands for the Agreement between the Swedish state and some county councils on cooperation on basic education of doctors, medical research and health care development).

**Appendix**

- Parental informed consent (in Swedish)

